4.0 Study Objectives

The objectives of the Phase 1 portion of the study include:

- Safety assessment
- Dose limiting toxicity (DLT) determination
- Maximum tolerated dose (MTD) determination

- Recommended Phase 2 Dose (RPTD) and schedule determination
- Pharmacokinetic profile evaluation

The objectives of the Phase 2a portion of the study include:

- Safety assessment at the recommended Phase 2 dose (RPTD) and schedule
- Preliminary efficacy assessment including biomarker assessment
- Pharmacokinetic profile evaluation

The objectives of the Extension Study portion of the study include:

- Safety assessment
- Evaluation of data regarding progression free survival (PFS) and overall survival (OS)

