Subjects will be evaluated against the NCI-WG (1996) criteria³⁰ and the IWCLL updated NCI-WG (January 2008) criteria³¹ (physical examination/CT/MRI) at the end of Cycle 2, the end of Cycle 4, end of every 4 cycles through Cycle 20 (i.e., C8, C12, C16, C20), end of every 8 cycles thereafter (i.e., C28, C36, C44. . .) and at the Final Visit. For the Extension Study, subjects will be evaluated against the NCI-WG (1996) criteria and the IWCLL updated NCI-WG (January 2008) criteria (physical examination/CT/MRI) at the Final Visit. Analysis of peripheral blood will be evaluated against the NCI-WG criteria for tumor response assessment on Day 1 (pre-dose) of the following cycle for every tumor assessment. For example, when a subject completes Cycle 2, the laboratory values from Day 1 of Cycle 3 (pre-dose) will be used to assess tumor response.

The tumor assessment performed at Screening will serve as the baseline for clinical assessment. Assessments for tumor response will be repeated 2 months after NCI-WG (1996) criteria for complete remission (CR) are first met and/or at least 2 months after the IWCLL updated NCI-WG (2008) criteria for complete remission (CR or CRi) are first met. Assessments for tumor response will be repeated at least 2 months after criteria for a partial remission (PR) are first met. Response criteria will be assessed while

subjects continue treatment with ABT-263. Response criteria definitions are outlined in Section 5.3.3.1.

Disease Progression Assessment (Extension Study)

Subjects should be evaluated for disease progression at a minimum of every 4 cycles and as deemed appropriate by the investigator per standard of care for tumor assessments. At each visit, the investigator should assess whether or not there is evidence of disease progression and record the date of progression on the paper Case Report Form if applicable. If a CT scan, MRI, or bone marrow aspirate or biopsy is performed per standard of care, the data should be recorded on the appropriate paper Case Report Form. Subjects exhibiting disease progression should be discontinued from the study per Section 5.4.1.

Pregnancy Test

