For female subjects of childbearing potential, the local reference laboratory will perform a serum pregnancy test at Screening and a urine pregnancy test before dosing on Cycle 1 Day 1 (14/21 day dosing schedule) or Lead-in Day 1 (21/21 day dosing schedule), if it has been > 7 days since obtaining the serum pregnancy test results. The test results must be reviewed and determined to be negative prior to dosing.

Subjects considered not of childbearing potential must be documented as being surgically sterile or post-menopausal (for at least 1 year).

Survival (Phase 2a)

Survival information (i.e., the date and cause of death, post-treatment cancer therapies, etc.) will be collected at 3 month intervals after the last study visit for a period of 2 years after the subject has discontinued from the study. In Protocol Amendment #12 this information will be no longer collected.

Clinical Laboratory Tests

Phase 1

In the Phase 1 portion of the study, local laboratories will be utilized to process and provide results for the clinical laboratory tests. Subjects who move into the Extension Study from Phase 1 will continue to use local laboratories for the clinical laboratory tests. The principal investigator or sub-investigator will review, initial and date all laboratory results. The laboratory test results will be collected on the electronic Case Report Forms. The laboratory test results from the Extension Study will be collected on paper Case Report Forms.

Hematology, chemistry and urinalysis samples will be collected at Screening, Cycle 1 Day 1, Cycle 1 Days 2 and 3 (chemistry and hematology only), weekly through the first 2 cycles, Day 1 of each subsequent cycle (or within 72 hours prior), at the Final Visit and at the Safety Follow-up Visit.

For the Extension Study, hematology and chemistry will be collected at Day 1, every 4 cycles (e.g., Cycle 4 Day 1, Cycle 8 Day 1, etc.), Final Visit and at the Safety Follow-up Visit.

During the lead-in period, hematology, chemistry and urinalysis samples will also be collected on Lead-in Day 1 and Lead-in Days 2 and 3 (chemistry and hematology only).

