In the event that a subject withdraws or is discontinued from the study, reason(s) for the discontinuation from the study will be recorded. A physical examination, ECG, echocardiogram, vital signs measurement, laboratory analyses, performance status assessment, collection of unused study drug, an assessment of adverse events and tumor assessment (if needed) will be performed as soon as possible after discontinuation from the study.

A Safety Follow-up Visit should be performed for all subjects approximately 30 days following discontinuation of ABT-263 and then as clinically appropriate for safety assessment. The subject will be followed until a satisfactory clinical resolution of the adverse event(s) is achieved. If the subject refuses a follow-up visit or the visit is not performed, the reason should be noted in the subject's source documentation.

In the event of a positive pregnancy test for a subject during the study, the administration of study drug to that subject must be discontinued immediately. The investigator will report the positive pregnancy test result by telephone within 1 working day to the contact listed in Section 6.5.

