8.1.3 Exploratory Efficacy

The following exploratory efficacy analyses will be performed on the data collected from the Phase 2a portion of the study.

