8.1.3.1 Progression-Free Survival

The distribution of PFS will be estimated using Kaplan-Meier methodology. Median time to PFS and the corresponding 95% confidence interval will be estimated.

For a given subject, PFS will be defined as the number of days from the date the subject started study drug to the date the subject experiences an event of disease progression, as defined in Section 5.3.3, or to the date of death if disease progression is not reached. All events of disease progression will be included, regardless of whether the event occurred while the subject was still taking study drug or had previously discontinued study drug. Events of death will be included for subjects who had not experienced disease progression provided the death occurred within 2 cycles (42 days) of the date of the last available tumor evaluation. If a subject has not experienced an event of disease progression or death as defined above, then the subject's data will be censored at the date of the last available evaluation for disease progression. The date of the last available evaluation will be the date of the last study visit at which a tumor assessment was performed.

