For a given subject, PFS was defined as the number of days from the date the subject started study drug to the date the subject experiences an event of disease progression, or to the date of death if disease progression was not reached. All events of disease progression were included, regardless of whether the event occurred while the subject was still taking study drug or had previously discontinued study drug. Events of death were included for subjects who had not experienced disease progression provided the death occurred within 2 cycles (42 days) of the date of the last available tumor evaluation. If a subject had not experienced an event of disease progression or death as defined above, then the subject's data was censored at the date of the last available evaluation for disease progression. The date of the last available evaluation was the date of the last study visit at which a tumor assessment was performed.

Response Rate

- Objective Response Rate (ORR)
 - Phase 1: $ORR = CR + PR$.
 - Phase 2: $ORR = CR + CR_i + PR$.

- Best Response Rate
 - Phase 1: Complete Response (CR), Partial Response (PR), Stable Disease (SD), Disease Progression (PD), and Incomplete Data (ID) were reported.
 - Phase 2: Complete Response (CR), Complete Response - incomplete bone marrow (CRi), Partial Response (PR), Stable Disease (SD), Disease Progression (PD), and Incomplete Data (ID) were reported.
- Disease Control Rate (DCR)
 - Phase 1: $DCR = CR + PR + SD$.
 - Phase 2: $DCR = CR + CRi + PR + SD$.

The exact binomial distribution was used to construct this confidence interval for the response rates, and the corresponding 95% confidence interval was constructed.

Time to Tumor Progression

Time to tumor progression for a given subject was defined as the number of days from the date the subject started study drug to the date of the subject's tumor progression. Time to tumor progression was collected up to 2 cycles (42 days) following the date of the last available tumor evaluation. All events of tumor progression were included, regardless of whether the event occurred while the subject was still taking study drug, or after the subject discontinued study drug. If a subject had not progressed, then the data was censored at the date of the last study visit at which a tumor assessment was performed.

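### Extension PFS counts progressions found at 4-cycle checks but credits event-free time only up to a tumor assessment, so the tail of the curve can be biased in either direction

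*Protocol*

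**What the plan says.** Protocol Section 4.0 lists PFS and OS, beside safety, among the Extension objectives. Section 8.1.3 opens with "The following exploratory efficacy analyses will be performed on the data collected from the Phase 2a portion of the study"; the SAP applies the same analyses to Phase 1 and Phase 2. Neither document gives a separate PFS definition for the Extension.

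Section 8.1.3.1 sets the rule:

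- **Events.** "All events of disease progression will be included", whether or not the subject is still on drug. A death without progression counts only if it falls no more than 42 days after the latest tumor evaluation.
- **Censoring.** "The date of the last available evaluation will be the date of the last study visit at which a tumor assessment was performed". The SAP, under Progression-Free Survival, repeats it: "The date of the last available evaluation was the date of the last study visit at which a tumor assessment was performed".

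The Extension schedule separates two procedures. Section 5.3.1.1 says "Subjects should be evaluated for disease progression at a minimum of every 4 cycles", and has the investigator judge progression at each visit and record the date of any progression. Appendix G places this Disease Progression Assessment on Day 1, every 4 cycles and at the Final Visit. Its Tumor Assessments row is ticked at the Final Visit only, with standard-of-care assessments recorded if a site does them. Section 5.4.1 says that at discontinuation "an assessment of adverse events and tumor assessment (if needed) will be performed". The Tumor Assessments row also carries the # mark used for virtual visits; the progression-check row does not.

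**The concern.** During Phase 1 and Phase 2a the scheduled tumor assessments both look for progression and supply the censoring date, so the rule is largely coherent. In the Extension the two roles come apart. A positive 4-cycle check gives an event at its date. A negative one leaves the subject's follow-up where the last tumor assessment put it. Length of follow-up then depends on outcome, which Kaplan-Meier estimation does not allow: subjects who progress late are in the late risk set, while comparable subjects who stay event-free may not be.

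The death rule works the other way. With tumor evaluations scheduled only at the Final Visit, most Extension deaths without progression would fall outside 42 days and be censored rather than counted.

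Treatment may continue for up to 11 years after the last subject enters the Extension, so the uncredited time per subject can be long. What is at stake is the late part of the PFS curve, the only part to which the Extension can add.

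**Working it through.** The documents give no PFS event target, power or assumed median, so there is no planned figure to reproduce. The check applies the written rule.

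**Intervals.** A cycle is 21 days. Death window: 2 × 21 = 42 days. Extension check interval: 4 × 21 = 84 days. Longest scheduled gap between tumor assessments before the Extension (every 8 cycles after Cycle 20): 8 × 21 = 168 days.

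**Worked example.** Take the 13 Extension subjects of Section 5.1 and measure from Extension entry. Let k progress at 4-cycle checks, and let a of the remaining 13 − k have a tumor assessment at the end. The others are censored at or before entry and leave the risk set before the first Extension event. With one event at a time, Kaplan-Meier telescopes to

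S(end) = a / (a + k).

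| k | a = 0 | half credited | all credited |
|---|---|---|---|
| 3 | 0/3 = 0 | 5/8 = 0.625 | 10/13 = 0.77 |
| 5 | 0/5 = 0 | 4/9 = 0.44 | 8/13 = 0.62 |
| 7 | 0/7 = 0 | 3/10 = 0.30 | 6/13 = 0.46 |

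With full credit the rule returns the correct proportion. With none, the curve must reach zero however few subjects progress.

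**Simulation with deaths.** Assumptions, none from the documents except n: n = 31 (the SAP's Phase 2 set); exponential PFS with median 18 or 30 months; Extension entry at 12 months; follow-up ending uniformly between 2 and 5 years; deaths without progression 0, 20 or 40% of events; 400 runs per scenario. Mean 3-year PFS under the written rule:

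| Event-free subjects with a Final Visit tumor assessment | Median 18 months (true 0.25); deaths 0 / 20 / 40% | Median 30 months (true 0.44); deaths 0 / 20 / 40% |
|---|---|---|
| 0% | 0.11 / 0.10 / 0.11 | 0.17 / 0.16 / 0.16 |
| 50% | 0.20 / 0.22 / 0.25 | 0.35 / 0.37 / 0.45 |
| 100% | 0.27 / 0.29 / 0.34 | 0.44 / 0.50 / 0.55 |

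The sign changes across the table. The top row is far too low. The bottom row is about right without such deaths and too high with them. In the middle row the two errors can cancel. (The 0.27 against 0.25 arises because progression is dated at the check that finds it.)

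**Repair in the same simulation.** Censoring at the last evaluation of either kind, and counting all deaths, gives 0.25 to 0.28 (true 0.25) and 0.44 to 0.45 (true 0.44), whatever share had a Final Visit assessment.

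**Effect on the median.** A median reached before Extension entry is untouched. A later one is not: with a 30-month median and no Final Visit assessments, 2-year PFS averages about 0.39 to 0.40 against a true 0.575, so the estimated median moves earlier.

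**The case against.** **The Final Visit tumor assessment is scheduled.** Section 5.3.1.1 and Appendix G schedule it for every Extension subject, and standard-of-care assessments are recorded too. This stands. A reader might infer that the long-term curve is simply biased downward. The documents do not support that: subjects with a Final Visit assessment are credited in full, and the 42-day rule pushes upward. Downward bias needs event-free subjects without a later assessment: at a data cut before Final Visits, after a discontinuation where it was judged unnecessary, or after a virtual Final Visit. The last two are possible rather than certain. Section 5.4.1 is general text. The # mark is given two meanings in Section 5.3.1.1 (may be done virtually; need not be done at a virtual visit), and the Appendix G key gives only the first, adding home visits.

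**The rule first speaks more broadly.** Before the sentence quoted, Section 8.1.3.1 censors at the last evaluation for progression, which would fit the 4-cycle check. But the next sentence defines that date by the tumor assessment, and the SAP keeps the definition.

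**Scope.** Section 8.1.3 is limited to Phase 2a data, so an Extension PFS curve is not expressly planned. That is true, but subjects keep their number on entering the Extension, PFS runs from first dose, and all progressions count. If Extension data are excluded, the Section 4.0 objective has no analysis.

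**How old the censoring date can be.** A reader might infer that the last tumor assessment can precede Extension entry by years. The schedule does not support this: assessments before entry are at most 168 days apart. It is the gap between that assessment and the last negative check that can reach years.

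**OS.** Of post-study survival information, Section 5.3.1.1 says "In Protocol Amendment #12 this information will be no longer collected". A reader might infer that OS should be censored at Amendment 12. That does not follow. This follow-up was for Phase 2a only and lasted 2 years, so Phase 1 subjects never had it, and such censoring would discard later deaths that Section 8.1.3.4 counts.

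**Conclusion.** The mismatch is in the text of both documents and should be corrected. In the Extension, events come from one procedure and censoring dates from another, and the death window follows the second. The late PFS curve can be too low wherever event-free subjects lack a later tumor assessment, and too high where deaths without progression fall outside 42 days. If every event-free subject has a Final Visit tumor assessment, there is no downward bias.

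The directions follow from the rule. The sizes do not come from the documents: they depend on the assumed PFS distribution, time of Extension entry, share of deaths and share of completed Final Visit assessments. In the cases examined, 3-year PFS ranged from 0.16 to 0.55 around a true 0.44, and from 0.10 to 0.34 around a true 0.25.

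The consequence is limited. Efficacy is exploratory, the Extension has about 13 subjects from both phases, and the only PFS summary named besides the curve is the median with its confidence interval. The effect falls mainly on the tail, not on a median reached before Extension entry.

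**What to change.** In Section 8.1.3.1 and the SAP:

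1. Define the last evaluation for disease progression as the later of the last tumor assessment and the last Extension Disease Progression Assessment recorded as no progression.
2. Use that one date both for censoring and as the start of the 42-day death window. Moving only the censoring date would credit event-free time while leaving most Extension deaths uncounted.
3. State that Extension data from Phase 1 and Phase 2a subjects feed the PFS analysis, and at what data cut.
4. Apply the same date to time to tumor progression (Section 8.1.3.3, including its own 42-day limit) and duration of overall response (Section 8.1.3.5).
5. Report the current rule as a sensitivity analysis.

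One limit remains. With checks 84 days apart, a 42-day window leaves 84 − 42 = 42 days of each interval uncovered. The simulated repair counted all deaths, so it shows somewhat less upward bias than this wording would. A further sensitivity analysis counting every death without prior progression would show the difference.

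The cost is wording and a rerun of the Kaplan-Meier estimates; no new procedure or visit is needed. The checks are already made at Extension visits, but the protocol explicitly asks only for the date of a progression, so the sponsor should confirm that the paper CRF also holds the date of a negative check. The small downside is that later follow-up would rest on investigator checks without scheduled imaging. No change to OS censoring is proposed.

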 - j. The specific laboratory tests required for chemistry, hematology and urinalysis are listed in [Table 7](#). Triglycerides will only be collected at Screening and at the Final Visit. Amylase and lipase will be collected at Screening, Cycle 1 Day 15, and Final Visit. For any subjects who are at high risk for tumor lysis syndrome (TLS) during Cycle 2 and beyond, additional samples for hematology and chemistry may be collected as per the management guidelines in Section [6.7.4](#).
 - k. Assessment for tumor response will be performed at the end of Cycle 2, end of Cycle 4, end of every 4 cycles through Cycle 20 (i.e., C8, C12, C16, C20), end of every 8 cycles thereafter (i.e., C28, C36, C44. . .) and at the Final Visit. Analysis of peripheral blood for tumor response will be performed on Day 1 (pre-dose) of the following cycle for every tumor assessment.
 - l. A CT scan will be performed at Screening (within 21 days prior to study drug administration).
 - m. Assessments for tumor response will be repeated 2 months after NCI-WG (1996) criteria for a complete remission (CR) are first met and/or at least 2 months after IWCLL updated NCI-WG (2008) criteria for a complete remission (CR or CRi) or partial remission (PR) are first met.
 - n. If clinical and laboratory criteria for a CR or PR are met), a bone marrow aspirate/biopsy and CT scan should be performed at least 2 months after the criteria are first met in order to confirm a CR or PR. A bone marrow aspirate/biopsy will be performed at the end of Cycle 8 (for all subjects regardless of response) if the subject is continuing to receive ABT-263.
 - o. Bone marrow aspirate/biopsy will be done at Screening (within 21 days prior to study drug administration) unless a bone marrow aspirate and biopsy was obtained within 12 weeks of starting study drug without intervening treatment and is representative of the subject's existing disease.
 - p. Serious adverse event assessment will be performed at Screening after informed consent has been obtained.
 - q. Adverse events will be followed until satisfactory clinical resolution of the adverse event is achieved.
 - r. Survival assessments will be collected every 3 months for 2 years following discontinuation from the study (including the extension portion of the study). In Protocol Amendment #12 this information will no longer be collected.

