8.1.3.3 Time to Tumor Progression

Time to tumor progression for a given subject will be defined as the number of days from the date the subject started study drug to the date of the subject's tumor progression. Time to tumor progression may be collected up to 2 cycles (42 days) following the date of the last available tumor evaluation. All events of tumor progression will be included,

regardless of whether the event occurred while the subject was still taking study drug, or after the subject discontinued study drug. If a subject has not progressed, then the data will be censored at the date of the last study visit at which a tumor assessment was performed.

The distribution of the time to tumor progression will be estimated using Kaplan-Meier methodology. Median time to tumor progression and the corresponding 95% confidence interval will be estimated.

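### Some deaths before the first on-treatment tumor assessment are not PFS events, and PFS and TTP have no censoring rule for subjects assessed only at Screening

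*Protocol*

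**What the plan says.** **Origin and censoring.** Protocol Section 8.1.3.1 sets the origin: "PFS will be defined as the number of days from the date the subject started study drug". The censoring rule applies "If a subject has not experienced an event of disease progression or death as defined above", and its date is fixed as follows: "The date of the last available evaluation will be the date of the last study visit at which a tumor assessment was performed". The SAP repeats this under Progression-Free Survival: "The date of the last available evaluation was the date of the last study visit at which a tumor assessment was performed". For TTP, Protocol Section 8.1.3.3 says that "the data will be censored at the date of the last study visit at which a tumor assessment was performed". None of these rules is limited to post-baseline visits.

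**Screening counts as a tumor assessment.** Section 5.3.1.1 (Tumor Assessments) states: "The tumor assessment performed at Screening will serve as the baseline for clinical assessment". Footnote l of Table 3 gives its timing: "A CT scan will be performed at Screening (within 21 days prior to study drug administration").

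**Deaths.** Without prior progression, a death is a PFS event only if it falls within two cycles (42 days) of the last tumor evaluation (Protocol 8.1.3.1 and SAP). Section 5.3.3.1.3 (Phase 2a) separately lets the investigator declare clinical progression without a scan, and lists death from disease progression among its forms. Section 8.1.3.7 places early death from malignant disease, toxicity or another cause in response categories 6 to 8 and treats these as treatment failure, labelled disease progression.

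**Schedule and analysis set.** The first scheduled on-treatment tumor assessment is at the end of Cycle 2. Table 3 with its footnote k, and Section 5.3.1.1, also schedule one at the Final Visit; Section 5.4.1 makes it conditional on need when a subject discontinues. The SAP (Data Sets Analyzed) reports all 31 Phase 2 and all 29 Phase 1 treated subjects as analyzed for efficacy.

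**The concern.** The censoring date can precede the time origin. A subject who leaves early with neither an event nor a post-baseline assessment has Screening as the last visit with a tumor assessment, and so gets a zero or negative time. A subject with a negative time is never at risk, so the number at risk at time zero would fall short of the 31 or 29 subjects the SAP says were analyzed.

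The same dependence on Screening affects deaths. If Screening is the last tumor evaluation, the 42-day window starts before treatment does and closes well before the first on-treatment assessment is due. A death after it closes is not an event, and the subject's time goes back to the Screening date. Here actual failures leave the PFS estimate, while Section 8.1.3.7 counts the same deaths as failures in the response classification.

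**Working it through.** **Inputs.** Cycle length 21 days (Protocol 5.1). Lead-in 7 days planned, with platelet-based extension to 14 days (5.1); no lead-in on the Phase 1 14/21 schedule. Screening scan up to 21 days before first dose (Table 3, footnote l). First on-treatment assessment at the end of Cycle 2. Phase 2 N = 31 and Phase 1 N = 29 (SAP).

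**Step 1: the plan's own figure.** 2 cycles × 21 days = 42 days, which matches the stated window.

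**Step 2: first on-treatment assessment, in days after first dose.**
- 21/21 schedule, 7-day lead-in: 7 + 42 = about day 49.
- 21/21 schedule, 14-day lead-in: 14 + 42 = about day 56.
- 14/21 schedule: about day 42.

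**Step 3: event-free subject assessed only at Screening.** Let s be the days from the Screening assessment to first dose. The censoring time for PFS and TTP is -s, which ranges from 0 to -21. The SAP's own day convention (Definition of Rx Days) also makes pre-dose time points negative.

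**Step 4: deaths.** With Screening as the last evaluation, a death d days after first dose is a PFS event only if d + s ≤ 42, that is, d ≤ 42 - s. Otherwise, unless progression is recorded, the subject is censored at -s.

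| s | Last death day counted | Deaths not counted, 7-day lead-in | Deaths not counted, 14/21 schedule | Time assigned |
|---|---|---|---|---|
| 1 | 41 | about 42 to 49 | about 42 | -1 |
| 7 | 35 | about 36 to 49 | about 36 to 42 | -7 |
| 14 | 28 | about 29 to 49 | about 29 to 42 | -14 |
| 21 | 21 | about 22 to 49 | about 22 to 42 | -21 |

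At s = 21 the first on-treatment assessment comes 21 + 49 = 70 days after Screening, against a window of 42.

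**Step 5: effect of the censoring date for living subjects.** The Kaplan-Meier estimate is the product of (1 - deaths or progressions / number at risk) over event times. A subject with time -21, 0 or 1 is in no risk set for an event after day 1, so every factor is the same whether that subject is dropped, left negative, or censored at day 0 or 1. A check on invented data for 31 subjects, of whom 1, 2, 3 or 5 had only a Screening assessment, agreed: for each count the median was identical under all four treatments. Only the number at risk at time zero changed, for example 28 instead of 31 with three such subjects.

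**Step 6: effect of uncounted deaths.** Suppose k uncounted deaths are restored as events and no other event or censoring comes first. PFS just after them is (31 - k)/31 instead of 100%.
- k = 1: 30/31 = 96.8%, a fall of 3.2 points.
- k = 3: 28/31 = 90.3%, a fall of 9.7 points.

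Later values are multiplied by the same factor: 50% becomes 50% × 30/31 = 48.4% for k = 1. In Phase 1 one death is 1/29 = 3.4 points overall. The range of 0 to 3 is an assumption, because the documents give no count.

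**The case against.** **Many early failures already have a valid time.** A reader might infer that anyone with only a Screening assessment is censored before first dose. The text does not support that. Investigator-declared clinical progression in Phase 2a and a death within 42 days of Screening are PFS events with positive times. This stands, and it limits the point to subjects with neither.

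**The Final Visit should supply an assessment.** Table 3, its footnote k and Section 5.3.1.1 all schedule one. This also stands: a living subject is affected only if that assessment is missed or judged unnecessary under Section 5.4.1. It gives little protection for a subject who dies before any Final Visit takes place.

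**A baseline scan cannot evaluate progression.** On this view the PFS wording already means post-baseline assessments, or includes the clinical progression checks made in Cycles 1 and 2. But Section 8.1.3.1 itself defines the date by the last visit with a tumor assessment, Table 3 lists clinical progression assessment on a separate row, and the TTP rule does not speak of evaluation for progression. If Screening is excluded, a subject with no later assessment has no censoring date at all, so a rule is still missing.

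**Losing early leavers flatters the curve.** This inference is tempting, but Step 5 shows it fails for living subjects: dropping them gives the same estimate as censoring them at Day 1. Any bias from informative early withdrawal would remain after the censoring fix. The argument holds only for uncounted deaths.

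**Response and PFS are different analyses.** Section 8.1.3.7 governs response, so it does not by itself define a PFS event. Even so, it labels early deaths of every cause as disease progression, which cannot easily be squared with censoring some of them before treatment began.

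**Conclusion.** The point holds in two parts of unequal weight.

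- **Missing default (minor).** For event-free subjects with no post-baseline assessment, the literal rule gives 0 to -21 days for both PFS and TTP. It leaves the Kaplan-Meier curve and median unchanged and affects only the number at risk and its agreement with the stated analysis set.
- **Uncounted early deaths (consequential, PFS only).** With Screening at day -21, a death not attributed to progression from day 22 to about day 49 (about day 42 on the 14/21 schedule) is excluded as an event. Each one restored lowers early Phase 2a PFS by about 3.2 points, assuming no earlier event or censoring. TTP is not affected, since death is not a TTP event.

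A reader might also infer that subjects were in fact lost from the reported analyses. Nothing in the documents shows this: the SAP reports all treated subjects as analyzed, and no count of affected subjects is given. The efficacy endpoints are exploratory and the sample size does not rest on PFS, so severity is low to moderate.

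**What to change.** 1. In Protocol 8.1.3.1 and the SAP, state that a death before the first scheduled post-baseline tumor assessment is a PFS event, however long after Screening it occurs.
2. In Protocol 8.1.3.1, Protocol 8.1.3.3 and the SAP, state that a subject with no event and no post-baseline tumor assessment is censored at Day 1 and kept in the number at risk.
3. Report how many subjects each sentence affects, by phase. If the first affects none, the PFS curve stands as it is.

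The cost is one or two sentences in the endpoint derivations. No new data are needed. Only the first sentence can change the PFS estimate; the second brings the number at risk into line with the 31 and 29 subjects reported.
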